### **7.5 Handling of clinical laboratory test values less than the limit of quantification**

If the measured values are reported to be not more than the limit of quantification, less than the limit of quantification, or impossible to calculate, the following handling procedures should be applied for tabulation, and missing values or zero values should not be used.

[Handling of quantification limit values]

- (1) If the measurement is reported as less than the limit of quantification

The value obtained by adding the following processing to the quantification limit value is used as an alternative value for tabulation.

- 1) After checking the number of significant figures of the applicable item, 1 should be subtracted from the significant figure of the lowest reported quantification limit value.
- 2) It should then be expanded by one digit to a smaller number and 9 is set.

Example) Report: <3 Significant figures of the measuring facility: up to ones digit  
→ Tabulation handling: 2.9

Report: <500 Significant figures of the measuring facility: up to tens digit  
→ Tabulation handling: 499

- (2) When the measured value is reported as not more than the limit of quantification or not less than the upper limit of quantification, the limit of quantification itself should be used as a substitute value for tabulation.

Example) Not more than the limit of quantification

Report:  $\leq 10$  → Tabulation handling: 10

Not less than the limit of quantification

Report:  $\geq 20$  → Tabulation handling: 20

## 7.6 Handling of PK-related data

The permitted range of blood sampling days for plasma drug concentration measurements should be set as described in “Table 9.1-1 Permitted ranges for study visits” in the study protocol. When it is necessary to examine the handling of data, such as when the day of blood sampling is outside the permitted range, when there is a deviation from the study protocol, or when the plasma collection procedure is not observed, the sponsor should decide whether to collect and analyze drug concentration data after the case review meeting.

## 8. Statistical Method

Data for up to Week 24 of the treatment period phase 1 will be fixed when all subjects have completed treatment period Phase 1. Statistical analysis will be conducted for the treatment period phase 1 fixed data.

### 8.1 Basic matters

#### 8.1.1 Level of significance and confidence coefficient

When implementing tests, level of significance should be set at 2-sided 5%. Confidence interval will be 2-sided with a confidence coefficient of 95%.

### 8.1.2 Descriptive statistics to calculate

Types of descriptive statistics items to be calculated for each continuous variable are provided below.

Number of subjects, mean, standard deviation (SD), median, minimum, maximum, and 2-sided 95% CI of the mean.

### 8.1.3 Number of digits displayed

The number of digits to be displayed in the analysis results will be as follows.

Numeric content	Number of display digits
p value	3 decimal places; however, when it is less than 0.001, it should be displayed as “<0.001”
Proportion (percentage)	Integer part + 1 decimal place
Rate of change	Integer part + 1 decimal place
Descriptive statistics (minimum and maximum)	Same as the number of digits in the original variable
Descriptive statistics (mean, SD, median)	Number of digits of the original variable + 1 digit
Hb value increase rate	Integer part + 4 decimal places
QOL (EQ-5D-5L) index value	Integer part + 3 decimal places

Hepcidin will be measured in units of pg/mL; however, the unit used for tabulation should be ng/mL, and the number of displayed digits should be two decimal places.

## 8.2 Breakdown of subjects

### 8.2.1 Disposition

For subjects enrolled in the treatment period, the breakdown of each analysis set in each treatment group should be provided.

Items: Number of subjects enrolled in treatment period, number of FAS subjects and its proportion, number of subjects excluded from FAS and its proportion, number of PPS subjects and its proportion, number of subjects excluded from PPS and its proportion, number of subjects in the safety analysis set and its proportion, number of subjects excluded from the safety analysis set and its proportion, number of subjects in the drug concentration analysis set and its proportion, and number of subjects excluded from the drug concentration analysis set and its proportion

### 8.2.2 Subjects who discontinued or interrupted their treatment

For subjects enrolled in the treatment period, the number and proportion of discontinued subjects should be tabulated in each treatment group and by reasons for discontinuation.

Items: Number and proportion of subjects who discontinued in each treatment group among those enrolled in the treatment period; number and proportion subjects who discontinued by reasons.

For subjects enrolled in the treatment period, the number of cases of interruption of MT-6548 tablets 150 mg in the MT-6548 group and darbepoetin alfa injection in the darbepoetin group should be tabulated by reasons for drug interruptions. The denominator of the proportion should be the sum of the number of drug interruptions. If there are multiple reasons for a single interruption, it should be counted for each reason and tabulated as the total number of interruption cases.

Items: Number of cases of interruption of MT-6548 tablets 150 mg/darbepoetin alfa injection in each treatment group among subjects enrolled in the treatment group; number and proportion of cases of interruptions by reasons.

### 8.3 Demographic and other baseline characteristics

The key demographic and other baseline characteristics for each analysis set (excluding the PK analysis set) should be summarized. Frequency and proportion will be provided for discrete variables and descriptive statistics for continuous variables (no calculation of 95% CI of the mean). If the PPS or safety analysis set is the same as the FAS, the results for the analysis sets will not be presented.

Table 8.3.1 Items relating to demographic and other baseline characteristics

Category	Item	Type of variables
Subject background	Sex (male, female)	Dichotomous
	Age (years) as of informed consent	Continuous
	2 categories: <65, ≥65	Dichotomous
	2 categories: <75, ≥75	Dichotomous
	Duration of nephrogenic anemia (years)	Continuous
	3 categories: <1, 1 to <5, ≥5	Ordinal
	Height (cm)	Continuous
	Dry weight (kg)	Continuous
	BMI (kg/m  )	Continuous
	2 categories: <25, ≥25	Dichotomous
	Race	
	3 categories: not Hispanic or Latino, Hispanic or Latino, Unknown	Polytomous

	Ethnicity 3 categories: Asian (Japanese), Asian (other), other	Polytomous
Smoking status	Presence or absence of smoking status 3 categories: never smoked, ex-smoker, current smoker	Polytomous
Underlying cause of CKD	Underlying cause 8 categories: diabetes mellitus, hypertension, autoimmune/glomerulonephritis/vasculitis, interstitial nephritis/pyelonephritis, cystic/hereditary/congenital disease, neoplasm/tumor, unknown, other	Polytomous
Complication	Presence or absence of complications on the first day of the treatment period	Dichotomous
	Presence or absence of hypertension	Dichotomous
	Presence or absence of diabetes mellitus	Dichotomous
	Presence or absence of dyslipidemia	Dichotomous
Previous ESA formulation	Type of previous ESA formulation 4 categories: epoetin (epoetin alfa, epoetin beta, or epoetin kappa), darbepoetin alfa, epoetin beta pegol, other	Polytomous
	Frequency of administration by type of previous ESA formulation 7 categories: once a week, twice a week, three times a week, every 2 weeks, every 3 weeks, every 4 weeks, other	Polytomous
	Weekly dose of epoetin alfa, epoetin beta, or epoetin kappa (IU)	Continuous
	Weekly dose of darbepoetin alfa (µg)	Continuous
	Weekly dose of epoetin beta pegol (µg)	Continuous
Evaluation data	Hb value (g/dL) on the first day of the treatment period 3 categories: <10, 10 to <11, ≥11	Continuous
	Liver function test (U/L) on the first day of the treatment period	Trichotomous
	3 categories: AST and ALT are both not more than the upper limit of normal, either is more than the upper limit of normal and both are not more than 2 times the upper limit of normal, either is more than 2 times the upper limit of normal	Trichotomous
	CRP (mg/dL) on the first day of the treatment period	Continuous
	Serum ferritin (ng/mL) on the first day of the treatment period 2 categories: <100, ≥100	Continuous
	2 categories: <100, ≥100	Dichotomous
	TSAT (%) on the first day of the treatment period 2 categories: <20, ≥20	Continuous
	With or without iron supplements on the first day of the treatment period 2 categories: oral, intravenous	Dichotomous
	With or without iron-containing phosphate binders on the first day of the treatment period	Dichotomous
Hemodialysis	Types of hemodialysis (2 categories: hemodialysis, hemodiafiltration)	Dichotomous
	Duration of hemodialysis (years)	Continuous
	Frequency of dialysis (2 categories: 3x per week, other)	Dichotomous

## 8.4 Study drug administration/treatment period and compliance status

For FAS and safety analysis set, the descriptive statistics of administration/compliance rate (no calculation of 95% CI of the mean) of MT-6548 tablets 150 mg/darbepoetin alfa injection should be calculated by treatment group to provide the number and proportion of subjects with administration/compliance rate of MT-6548 tablets 150 mg/darbepoetin alfa injection of  $\geq 80\%$  and  $< 80\%$ .

For FAS and safety analysis set, the descriptive statistics of the study drug administration/treatment period (no calculation of 95% CI of the mean) should be calculated by treatment group.

For FAS and safety analysis set, the descriptive statistics of the cumulative dosage of MT-6548 tablets 150 mg/darbepoetin alfa injection (no calculation of 95% CI of the mean) should be calculated by treatment group.

## 8.5 Efficacy analysis

As a general rule, efficacy analysis will be performed on the FAS. When necessary, descriptive statistics for continuous variables should be calculated and frequency and proportion will be calculated for discrete variables. No data from the day after the rescue therapy implementation date should be included in the efficacy analysis.

### 8.5.1 Analysis of primary endpoint

Descriptive statistics will be calculated for the primary efficacy endpoint of the mean Hb value at Week 20 and 24 of the treatment period. The MMRM is used to model the mean Hb values at each evaluation time point based on the following model, and the mean Hb values at Week 20 and Week 24 of the treatment period for each treatment group should be obtained. The least squares mean (hereinafter, LSMean), its standard error, and 2-sided 95% CIs for the mean Hb values should be calculated, and the point estimate of the between-group difference (MT-6548 – darbepoetin) of LSMean, its standard error, and 2-sided 95% confidence intervals should be calculated. When the lower limit of 95% CI of the difference between the groups is no less than  $-0.75$  g/dL, MT-6548 will be considered noninferior to darbepoetin alfa (recombinant).

[figure not shown]
The robustness of the results will be examined by the same analysis for PPS.

[MMRM Model]

- Covariate: response variable value of the first day of the treatment period

- Fixed effects: treatment group, evaluation time point, interaction of evaluation time point × treatment group
- Degrees of freedom adjustment: Kenward-Roger method
- Covariance matrix within subject for each subject: unstructured (type = UN; unstructured)  
If the within-subject variance-covariance matrix is not converged using unstructured data, the within-subject variance-covariance matrix should be changed in the following order, and the analysis should be performed using the within-subject variance-covariance matrix that is converged first.  
Heterogeneous Toeplitz (TOEPH) → Heterogeneous AR (1) (ARH [1]) → Heterogeneous CS (CSH) → Toeplitz (TOEP) → First-order autoregressive (AR [1]) → Compound symmetry (CS)
- Random effects: subjects

Sample SAS code

The non-inferiority of MT-6548 to darbepoetin should be assessed after confirming that the mean Hb values and its 95% CI of MT-6548 cohort at Weeks 20 and 24 of the treatment period are included within the target range ( $\geq 10.0$  g/dL and  $< 12.0$  g/dL) based on the MMRM model.

Sensitivity analysis should be evaluated using following analysis methods for FAS.

[figure not shown]
- The defect mechanism of the missing not at random is be assumed, and the tipping point analysis will be performed after 1000 times of multiple imputation using the fully conditional specification regression method. For the data with multiple imputation, a similar analysis should be performed using the same MMRM model as that used for the primary efficacy endpoint, mean Hb values at Week 20 and Week 24 of the treatment period. When non-inferiority is not

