3.2 Inclusion criteria

Subjects must meet all inclusion criteria below and have capacity to grant informed consent. Laboratory tests related to the inclusion criteria will be assessed based on central laboratory measurements. If a given laboratory test is performed multiple times during the screening period, the most recent test will be used for assessment. If blood is drawn on the day of dialysis, data obtained before dialysis will be used for assessment. In addition, Hb values in blood collected in the supine position will be used for assessment.

- (1) Patients at least 20 years of age as of the day of consent (either sex)
- (2) Patients with CKD diagnosed according to the Japanese Society of Nephrology's "Clinical Practice Guidebook for Diagnosis and Treatment of Chronic Kidney Disease 2012" as of the day of consent
- (3) Patients who have received either hemodialysis or hemodiafiltration three times a week for at least 12 weeks prior to the first day of the screening period; however, patients on home dialysis and those receiving a combined therapy of home hemodialysis and peritoneal dialysis are excluded
- (4) Patients receiving the same formulation of ESA using the same administration route and the same dose interval (the dose interval should be the one described in the package insert for the ESA formulation) in the 8 weeks prior to the first day of the screening period, using the dosages described below

Dosage:

- ✓ Epoetin alpha (recombinant), epoetin beta (recombinant), and epoetin kappa (recombinant): ≤ 9000 IU every week
- ✓ Darbepoetin alfa (recombinant): ≤ 60 μ g every week
- ✓ Epoetin beta pegol (recombinant): ≤ 250 μ g every 4 weeks

- (5) Patients with a mean Hb value (mean of the latest two measurements) of ≥ 9.5 g/dL and ≤ 12.0 g/dL during the screening period
- (6) Patients with an Hb difference of < 1.5 g/dL between the latest two measurements during the screening period
- (7) Patients with a serum ferritin value of ≥ 100 ng/mL or a transferrin saturation (TSAT) of $\geq 20\%$ during the screening period

- (8) Patients with folic acid and vitamin B₁₂ values above the lower limit of normal values during the screening period

Rationale

- (1) Individuals are legally capable of granting consent as of 20 years of age. There is no particular basis for limiting participation to either sex.
- (2) To ensure that subjects have the target disease of CKD.

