8.3.3 Maintenance dosage and dosage adjustments

(1) MT-6548 Tablet

Maintenance dosage is 150–600 mg once daily and adjusted according to the dosage

adjustment guideline below.

(2) Darbepoetin alfa injection

The maintenance dosage is 5–180 µg per dose once a week, once every 2 weeks, or once every 4 weeks, which will be adjusted as appropriate according to the dosage adjustment guidelines below.

[Dosage adjustment guidelines]

Investigators/subinvestigators will monitor Hb levels throughout the treatment period, and determine whether to adjust study drug dosage or discontinue administration as required. In principle, dosage adjustment will be performed at scheduled visits or on the day of darbepoetin alfa injection; however, an additional visit may be provided for dosage adjustment, if considered necessary, in cases where excessive increases or decreases in Hb levels are of concern based on the Hb time course. In principle, dosage of MT-6548 Tablets and darbepoetin alfa injection will be adjusted simultaneously. If interruption of study drug administration is necessary, administration of MT-6548 Tablets and darbepoetin alfa injection should be discontinued, and if study drug administration is resumed, administration of both drugs should be resumed.

Hb levels will be measured in samples collected in the supine position using a HemoCue® Hb201 DM analyzer; and in principle, these measurements will be used to determine dosage adjustments. Hb levels on the day of dialysis will be measured in samples collected before dialysis. Hb measurements used for dosage adjustment determinations will be recorded in the subject's CRF. Measurement results from the HemoCue® Hb201 DM will be used solely for determination of study drug dosage adjustments, and will not be used for efficacy or safety analysis.

The dosage adjustment algorithm below will be followed in order to maintain Hb levels of 10.0–12.0 g/dL during the study. Dosage steps are defined in the dosage adjustment table below.

MT-6548 Tablet dosage adjustment table

Step	No. of tablets	Dosage
1	1	150 mg or placebo
2	2	300 mg or placebo
3	3	450 mg or placebo
4	4	600 mg or placebo

Darbepoetin alfa injection dosage adjustment table

Step	Dosage
1	5 µg or placebo
2	10 µg or placebo
3	15 µg or placebo
4	20 µg or placebo
5	30 µg or placebo
6	40 µg or placebo
7	50 µg or placebo
8	60 µg or placebo
9	80 µg or placebo
10	100 µg or placebo
11	120 µg or placebo
12	140 µg or placebo
13	160 µg or placebo

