8.5.3 Rescue therapy

The following rescue therapy options will be provided as needed for subject safety. If any of the following rescue therapies is performed prior to the completion of the scheduled tests at Week 24 of the treatment period, that subject will be withdrawn from the study. If rescue therapies are performed after scheduled tests at Week 24 of the treatment period, the subject can continue in the study unless

investigators/subinvestigators determine study withdrawal is appropriate. Details of any rescue therapy implemented will be recorded in the subject's CRF.

(1) ESA formulations

If a subject has received maximum dosages of MT-6548 Tablets and darbepoetin alfa injection for ≥ 2 weeks and meets all criteria below, the investigator/subinvestigator may administer an ESA as a rescue therapy to improve Hb levels if necessary in order to secure subject safety. An ESA-based rescue therapy may also be provided without meeting the criteria below if the investigator/subinvestigator considers it necessary to secure subject safety, such as in cases of acute decreases in Hb levels. Study drug administration (MT-6548 Tablets and darbepoetin alfa injection) will be discontinued when an ESA-based rescue therapy is provided. Study drug treatment may be resumed after an improvement in Hb levels and should not be coadministered with a rescue therapy with an ESA. Subjects who are not expected to resume study drug treatment will be withdrawn from the study.

Administration of any ESA formulation other than the study drug is considered a rescue therapy. Dosage increase of the study drug darbepoetin alfa injection (including an increase not in accordance with the dosage adjustment algorithm) is not considered a rescue therapy.

- ✓ Anaemia or anaemia symptoms (e.g., fatigue, weakness, shortness of breath, chest pain, confusion, dizziness) become aggravated compared to the first day of the treatment period to the point they are clinically problematic.
- ✓ Hb levels drop to <8.0 g/dL.

(2) RBC transfusion

Usually, RBC transfusions are performed when clinically necessary in instances of acute or major bleeding. For less severe anemia, which may be exacerbated, or moderate to severe anemia symptoms, RBC transfusions may be performed as needed clinically at the discretion of the investigator/subinvestigator.

(3) Phlebotomy

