13.3.2 Efficacy

(1) Analysis methods for primary endpoint

For the primary endpoint of mean Hb at treatment period Weeks 20 and 24, mean Hb at each timepoint will be modeled using MMRM with the following model, mean Hb at treatment period Weeks 20 and 24 will be calculated for each group, and point estimates and their two-sided 95% CI will be calculated for differences in mean values between the MT-6548 group and the darbepoetin group. Non-inferiority of MT-6548 to darbepoetin alfa (recombinant) will have been established if the lower limit of the 95% CI is ≥ -0.75 g/dL.

[MMRM model]

- Covariates: Baseline values
- Fixed effects: Treatment group, evaluation period, interactions of evaluation period \times treatment group, Random effects: Subjects
-

The non-inferiority of the MT-6548 group with the darbepoetin group will be assessed after the mean of mean Hb values at treatment period Weeks 20 and 24 and its 95% CI is confirmed to fall within the target range of Hb values (10.0–12.0 g/dL).

Sensitivity analysis will be performed using the following analysis methods.

- 1) Tipping point analysis
- 2) ANCOVA using data with missing values imputed by LOCF and baseline values as covariates

(2) Analysis methods for secondary endpoints

1) Mean Hb at treatment period Weeks 48 and 52

Treatment groups will be compared using the same analysis methods (MMRM) used for the primary endpoint. Point estimates and their standard errors and 95% CI will be calculated for differences in mean values between the MT-6548 group and the darbepoetin group.

2) Hb at each treatment period timepoint

Descriptive statistics will be calculated for Hb levels at each treatment period timepoint, and analysis performed taking into account changes over time using MMRM.

3) Proportion of subjects with mean Hb levels within the target range (10.0–12.0 g/dL), <10.0 g/dL, and ≥ 12.0 g/dL at each timepoint in the treatment period

Numbers and ratios of subjects with mean Hb at each treatment period timepoint within

the target range (10.0–12.0 g/dL), <10.0 g/dL, and ≥ 12.0 g/dL will be shown.

(3) Other endpoints

Incidence and ratios will be shown for discrete data, while descriptive statistics will be calculated by treatment group for continuous data.

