### [Rationale]

For the primary efficacy endpoint of mean Hb values at treatment period Weeks 20 and 24, the mean Hb value in the darbepoetin group is assumed to be 11.0 g/dL, the difference between the MT-6548 and darbepoetin groups is assumed to be 0 g/dL, and the standard deviation for both is assumed to be 1.73 g/dL. The non-inferiority margin is set at -0.75 g/dL. Calculation of statistical power from these assumptions shows that a sample size of 150 subjects in each group would ensure greater than 95% probability that the mean of mean Hb values in the MT-6548 group and their 95% CI would fall within the target Hb range (10.0–12.0 g/dL) and non-inferiority could be established.

The assumed standard deviation was set at 1.73 g/dL based on the upper limit of the two-sided 95% confidence interval of the standard deviation in the MT-6548 300 mg group at Week 6 in study CI-0022.

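### As listed, the primary MMRM has one baseline-Hb slope for all visits; if the Week 20/24 slope differs from it, the non-inferiority CI is slightly wider than it need be (low priority, no error)

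*SAP*

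**What the plan says.** Phase 1 SAP 8.5.1 specifies an MMRM with an unstructured within-subject covariance and Kenward-Roger degrees of freedom. The baseline term is "Covariate: response variable value of the first day of the treatment period". The other terms are "Fixed effects: treatment group, evaluation time point, interaction of evaluation time point × treatment group".

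Protocol 13.3.2 gives the same structure: baseline values as covariate, then "Fixed effects: Treatment group, evaluation period, interactions of evaluation period" with treatment group. Final SAP 8.5.1 repeats it for the Week 48/52 mean. The errata attached to the SAP add no baseline-by-visit term.

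The sample-size rationale (protocol 6.1, SAP 2.4) states that "the standard deviation for both is assumed to be 1.73 g/dL". It uses a true difference of 0, a margin of -0.75 g/dL and 150 subjects per group, and claims a probability above 95%.

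The planned sensitivity ANCOVA in Phase 1 SAP 8.5.1 regresses the Week 20/24 mean directly on day-1 Hb, with missing values filled by LOCF.

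**The concern.** A main-effect covariate with no visit interaction makes one number describe how strongly day-1 Hb predicts Hb at Week 2 and at Week 24. This trial gives a reason to doubt that. Protocol 8.3.3 says "The dosage adjustment algorithm below will be followed in order to maintain Hb levels of 10.0–12.0 g/dL during the study", and both arms follow that algorithm. Repeated titration toward a common range could weaken the link between baseline and later Hb. The common slope is estimated from all nine Phase 1 visits, so it could then be wrong for the two visits that form the endpoint.

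What is at stake is precision only. Part of the baseline-related variation at Weeks 20 and 24 would be over- or under-corrected and left in the residual, which widens the CI whose lower limit is compared with -0.75 g/dL.

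**Working it through.** **1. The plan's own figure.** With SD 1.73 and 150 per group, SE = 1.73 × √(2/150) = 0.1998. Power = Φ(0.75/0.1998 − 1.96) = 96.4%. The additional condition, that the MT-6548 mean and its CI lie within 10.0-12.0 g/dL, is met almost surely: the group SE is 1.73/√150 = 0.141, and 1.0/0.141 − 1.96 ≈ 5.1. By simulation the joint probability is 96.3%, so the claim of more than 95% reproduces. The unadjusted CI half-width is 1.96 × 0.1998 = 0.392 g/dL.

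**2. Cost of a common slope.** Let b be the vector of visit-specific baseline slopes, S the residual covariance of the nine visits (Weeks 2, 4, 6, 8, 10, 12, 16, 20, 24) and L the average of Weeks 20 and 24. Under an unstructured covariance the fitted common slope is c = 1'S⁻¹b / 1'S⁻¹1. The per-subject variance of the endpoint is:

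- visit-specific slopes: L'SL
- common slope: L'SL + (L'b − c)² × Var(baseline)
- no baseline adjustment: L'SL + (L'b)² × Var(baseline)

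If all slopes are equal, L'b = c and the cost is zero.

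**3. Inputs.** From the documents: SD 1.73, 150 per group, margin 0.75, the visit schedule. Assumed, because the documents give none of them:

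- Baseline SD 0.7. The only handle is the screening window (protocol 3.2): "Patients with a mean Hb value (mean of the latest two measurements) of" 9.5 to 12.0 g/dL; a uniform spread over it has SD 2.5/√12 = 0.72.
- 4-week correlation 0.6 to 0.9, with 10% or 20% short-term noise.
- How the SD grows from baseline: linearly to Week 24, or level from Week 6. In each case the Week 24 SD is solved so that the Week 20/24 mean has SD 1.73.

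**4. Results** (slope = slope at Weeks 20/24, c = fitted common slope; power uses the common slope and complete data)

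| Corr. | Noise | Linear: slope / c | CI wider | Power | Level: slope / c | CI wider | Power |
|---|---|---|---|---|---|---|---|
| 0.6 | 10% | 0.16 / 0.72 | 2.6% | 95.6% | 0.16 / 0.94 | 4.9% | 94.8% |
| 0.6 | 20% | 0.14 / 0.63 | 1.9% | 95.8% | 0.14 / 0.83 | 3.8% | 95.2% |
| 0.7 | 10% | 0.35 / 0.83 | 1.9% | 96.1% | 0.35 / 1.07 | 4.3% | 95.3% |
| 0.7 | 20% | 0.32 / 0.73 | 1.4% | 96.2% | 0.32 / 0.96 | 3.3% | 95.6% |
| 0.8 | 10% | 0.70 / 0.92 | 0.4% | 97.4% | 0.71 / 1.20 | 2.1% | 97.0% |
| 0.8 | 20% | 0.64 / 0.83 | 0.3% | 97.2% | 0.64 / 1.09 | 1.7% | 96.9% |
| 0.9 | 10% | 1.31 / 1.00 | 1.1% | 99.2% | 1.31 / 1.31 | 0.0% | 99.3% |
| 0.9 | 20% | 1.19 / 0.90 | 0.9% | 98.9% | 1.20 / 1.22 | 0.0% | 99.0% |

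First row, linear, by hand: visit-specific residual SD 1.727; slope gap 0.155 − 0.721 = −0.566; 1.727² + (0.566 × 0.7)² = 2.983 + 0.157 = 3.140; SD 1.77, ratio 1.026. The half-width goes from 0.391 to 0.401 g/dL. First row, level: gap −0.784; 1.726² + (0.784 × 0.7)² = 2.979 + 0.301 = 3.280; SD 1.81, ratio 1.049; half-width 0.410 g/dL.

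**5. How far these ranges carry.** Power falls below 95% once the SE passes 0.75/(1.96 + 1.645) = 0.2080, which is 4.1% above 0.1998. One of the 16 settings does so. Other fade patterns and residual correlations with baseline SD 0.72 gave 0.1-6.6%, with scenario medians of 0.2-1.3%. None of these figures is a ceiling.

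**6. Is the reported SE honest?** Unstructured-covariance fits were simulated (600 trials, 150 per group, baseline SD 0.72, slope fading from 1 toward 0, residual variance growing). The common-slope model reported an average SE of 0.2053, against an empirical SD of 0.2037 for its estimates. The misfit is absorbed into the residual variance.

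**The case against.** The strongest reply is that this is a preference. A main-effect baseline covariate with unstructured covariance is valid, its SE is honest, and randomization protects the contrast. That stands, and it is why the point is low priority.

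The premise could also be an artefact of publication, since the sample SAS code under the model is not shown. The point therefore concerns the model as listed.

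The planned ANCOVA already has a slope specific to the endpoint, and on complete data it would reach the precision asked for here. That largely stands. Because it runs on LOCF data, it is not a full substitute, and a gap between it and the MMRM would mix slope handling with missing-data handling.

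The loss is largest where baseline hardly predicts the endpoint: at 4-week correlation 0.6-0.7 the implied correlation between baseline and the Week 20/24 mean is only about 0.06-0.14. In those settings the adjusted CI is slightly wider than an unadjusted one (0.394-0.401 against 0.392 g/dL with the linear SD), but by less than 0.01 g/dL. At correlation 0.9 with the linear SD the slope rises with time, so fading is not a given.

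A reader might go further and infer that rescue and dropout linked to low Hb turn this into bias in the primary estimate. The documents do not support that step. It needs Hb dips and dropout rates that differ by arm, and neither is given. The timing of formal ESA rescue cannot be fixed either: for the maximum-dosage condition, synopsis 6.3 joins the two study drugs with *or*, while protocol 8.5.3 joins them with *and*. Those two passages must be reconciled, but that is a separate matter.

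**Conclusion.** The point holds as a small, optional gain in precision. As listed, the model has one baseline slope for all visits, and a different slope at Weeks 20/24 makes the CI slightly wider than necessary. Under the stated assumptions the excess is 0.3-2.6% with a linear SD rise and 0.0-4.9% with the SD level from Week 6. Minimum power is 95.6% and 94.8% respectively, against 96.4% unadjusted. With equal slopes the excess is zero.

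Two stronger conclusions might be drawn and should not be. One is that the non-inferiority result is biased or its error rate inflated: on complete data there is no bias and the SE is honest. The other is that the claim of more than 95% power fails. It reproduces from the plan's own inputs, and the single setting just under 95% rests on assumed correlations and an assumed SD profile. The planning SD of 1.73 is itself an upper confidence limit.

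**What to change.** Add evaluation time point × baseline value to the fixed effects listed for the MMRM in protocol 13.3.2 and both SAPs. This adds 8 parameters in Phase 1 (nine visits) and 15 in the final model (16 visits), which is negligible with 300 subjects, and needs no new data.

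Final SAP 8.5.4.3 says the Phase 1 analysis has been conducted, so the term cannot now narrow the CI that decided non-inferiority. For Phase 1, keep the pre-specified model as the primary result. Report the extended model in one additional table, labelled as added after data lock and with the reason stated, as protocol 13.4 requires. If the program already contains the term, say so and correct the listed model instead. In the Week 48/52 model, which is not confirmatory, use the term for precision only.
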